9. DATA ANALYSIS METHODS

9.1. Determination of Sample Size

Up to approximately 414 subjects may be enrolled in the study, including up to 72 subjects in Part A (q3wk dosing) with each cohort having up to 12 subjects, up to 252 subjects in Part B (q1wk dosing) with each cohort having up to 30 subjects, and approximately 90 subjects in Part C (monotherapy or combination with pembrolizumab) with each arm having 30 subjects.

Additional cohorts may also be added in future protocol amendments for additional indications, alternative dosing schedule, biopsy/biomarker analysis, and LV based combination therapy.

The sample size is not based on power calculations for a formal hypothesis testing but is selected to provide a degree of characterization of commonly occurring AEs in the safety profile and/or a reasonable estimation precision of ORR.

For a sample size of 30 subjects per cohort/arm, assuming confirmed ORR is between 10% and 50%, and confirmed PSA response rate for CRPC is between 10% and 50%, the 2-sided 90% exact confidence interval (CI) are summarized below:

Confirmed ORR*	90% Exact CI (N=30)
10%	(3%, 24%)
20%	(9%, 36%)
30%	(17%, 47%)
40%	(25%, 57%)
50%	(34%, 66%)

*Including confirmed PSA response rate for CRPC cohort

This sample size of 30 subjects per cohort/arm would additionally provide the following probabilities of observing at least 1 patient having an AE, as summarized below.

True AE Incidence Rate	Probability of Observing at Least One Patient Having an AE (N=30)
5%	79%
10%	96%

In Part B, the initial 12 subjects enrolled across the tumor cohorts per dose level will be evaluated for safety after the 12th patient completes the first cycle of treatment. The sample size of 12 allows for a reasonable likelihood of observing a given AE in at least 1 subject even when the incidence of the specific AE is low.

The table below shows the probability of observing an AE in at least 1 subject out of 12 subjects for different underlying incidence of AEs.

Underlying AE Incidence	Probability of Observing the AE in 1 or More Subjects Out of 12 Subjects
1%	11%
5%	46%
10%	72%

9.2. Study Endpoint Definitions

9.2.1. Confirmed ORR

Confirmed ORR is defined as the proportion of subjects who achieve a confirmed CR or PR according to RECIST v1.1 as assessed by the investigator. Subjects who do not have at least 2 post-baseline response assessments (initial response and confirmation scan) will be counted as non-responders.

9.2.2. Confirmed PSA Response Rate

Confirmed PSA response rate is defined as the proportion of subjects with a reduction from baseline PSA level of at least 50%, measured twice ≥ 3 weeks apart.

9.2.3. Disease Control Rate

DCR is defined as the proportion of subjects who achieve a confirmed CR or PR according to RECIST v1.1 as assessed by the investigator, or meet the SD criteria at least once after start of study treatment at a minimum interval of 5 weeks or 7 weeks for prostate cancer subjects. Subjects who do not have at least 1 post-baseline response assessment will be counted as non-responders.

9.2.4. Duration of Response

DOR is defined as the time from the first documentation of objective response (CR or PR that is subsequently confirmed) to the first documentation of PD or death due to any cause, whichever comes first.

DOR data will be censored as described below:

- Subjects who do not have PD and are still on study at the time of an analysis will be censored at the date of last disease assessment documenting absence of PD.
- Subjects who started a new anticancer treatment prior to documentation of PD will be censored at the date of last disease assessment prior to the start of new treatment.
- Subjects who are removed from the study prior to documentation of PD will be censored at the date of last disease assessment documenting absence of PD.

DOR will only be calculated for subjects who achieve a confirmed CR or PR as measured by RECIST v1.1 for all tumors.

PSA-DOR is defined as the time from the first documentation of PSA response (subsequently confirmed at least 3 weeks apart) to the first documentation of PSA progression or death due to any cause, whichever comes first.

9.2.5. Progression-Free Survival

Progression-free survival (PFS) is defined as the time from the start of study treatment to the first documentation of PD by RECIST v1.1 or clinical PD or by PSA progression (prostate cancer cohort) or death due to any cause, whichever comes first. PSA-PFS is defined in Section [9.2.7](#).

The same censoring rules as outlined in Section [9.2.4](#) for DOR will be applied to PFS. Subjects lacking an evaluation of tumor response after their first dose of study drug will have their event time censored at Day 1.

9.2.6. Overall Survival

OS is defined as the time from the start of study treatment to date of death due to any cause. In the absence of death, survival time will be censored at the last date the subject is known to be alive (i.e., date of last contact).

9.2.7. Prostate-Specific Antigen Progression-Free Survival

PSA-PFS is defined as the time from the start of study treatment to first occurrence of PSA progression or death, whichever comes first.

9.3. Statistical and Analytical Plans

The statistical and analytical plans presented below summarize the more complete plans to be detailed in the statistical analysis plan (SAP). A change to the data analysis methods described in the protocol will require a protocol amendment only if it alters site conduct (eg, adding baseline assessments to define a subgroup). The SAP will be finalized prior to database lock. Any key changes to the methods described in the final SAP will be described in the clinical study report.

9.3.1. General Considerations

In general, descriptive statistics will be presented that include the number of observations, mean, median, standard deviation, minimum and maximum for continuous variables, and the number and percentages per category for categorical variables.

The 2-sided 90% exact CI using Clopper-Pearson method ([Clopper 1934](#)) will be calculated for the response rates where applicable (eg, ORR).

For time-to-event endpoints, the median survival time will be estimated using the Kaplan-Meier method; the associated 90% CI will be calculated based on the complementary log-log transformation ([Collett 1994](#)).

9.3.1.1. Randomization and Blinding

This is an open-label study. Blinding will not be performed. Cohorts in Part A and Part B are single-arm. The cohort in Part C has 3 randomized arms.

For Part C, approximately 90 subjects will be randomized to 1 of the 3 arms with 30 subjects per arm: Arm 1 (monotherapy 2q3wk), Arm 2 (2q3wk combination with pembrolizumab), Arm 3 (q1wk combination with pembrolizumab). The randomization ratio will be 2:1:1 until Arm 1 enrolls 30 subjects. This will ensure that Arm 1 reaches the target enrollment sooner. Thus, of the first 60 subjects, 30 subjects will be enrolled in Arm 1, 15 subjects will be enrolled in Arm 2 and 15 subjects will be enrolled in Arm 3. Afterwards, the remaining subjects will be randomized in a 1:1 ratio to either Arm 2 or Arm 3. Randomization will be stratified according to BRAF mutational status (wild-type versus mutated).

9.3.1.2. Adjustments for Covariates

No adjustments for covariates are planned in the analyses.

9.3.1.3. Handling of Dropouts and Missing Data

Missing data will not be imputed unless otherwise specified. Missing AE start date and/or end date will be imputed while calculating duration of events and treatment-emergent status. Missing subsequent anticancer treatment start date will be imputed while deriving the time-to-event endpoints as applicable. Censoring rules will be applied for the analysis of time-to-event endpoints. Details will be provided in the SAP.

9.3.1.4. Multicenter Studies

There are multiple centers in this study, however it is not anticipated that any center will accrue enough subjects to warrant an analysis by center.

9.3.1.5. Multiple Comparisons and Multiplicity

No multiple comparisons are planned in this study.

9.3.1.6. Data Transformations and Derivations

Time variables based on 2 dates (eg, start date and end date) will be calculated as (end date – start date +1 [in days]) unless otherwise specified in the planned analysis section.

Baseline values used in all statistical analyses will be the most recent non-missing measurement prior to the first dose of study drug unless otherwise specified.

9.3.1.7. Analysis Sets

The full analysis set (FAS) includes all subjects who received any amount of study drug. All efficacy analyses will be based on the FAS.

The safety analysis set includes all subjects who received any amount of study drug, and thus is equivalent to the FAS. All safety analyses will be based on the safety analysis set.

The efficacy evaluable analysis set includes subjects who received any amount of study drug and had at least one post-baseline disease assessment per RECIST v1.1 or had clinical progression per investigator judgment or discontinued from study.

The PSA evaluable analysis set includes subjects in the prostate cancer cohort who received any amount of study drug and had both baseline and at least one evaluable post-baseline PSA measurements.

9.3.1.8. Examination of Subgroups

As exploratory analyses, subgroup analyses may be conducted for selected endpoints. Detailed methodology will be provided in the SAP.

9.3.1.9. Timing of Analyses

The primary analysis will be conducted when all treated subjects in a cohort have been followed for at least 6 months or come off study, whichever comes first. Subsequent data cutoff dates may be defined to allow for more precise estimates of time-to-event endpoints.

Interim analysis for futility will be performed separately for each cohort in Part A and Part B after approximately 12 subjects of a given cohort have been treated and are efficacy evaluable post-baseline.

9.3.2. Subject Disposition

An accounting of study subjects by disposition will be tabulated and the number of subjects in each analysis set will be summarized. Subjects who discontinue study treatment and subjects who withdraw from the study will be summarized with reason for discontinuation or withdrawal.

9.3.3. Subject Characteristics

Demographics and other baseline characteristics will be summarized by cohort for the FAS. Details will be provided in the SAP.

9.3.4. Treatment Administration

Treatment administration will be summarized by cohort for the safety analysis set. Summary statistics for duration of therapy, number of cycles per subject, and the number and percentage of subjects treated at each cycle will be presented. Details will be provided in the SAP.

9.3.5. Efficacy Analyses

The primary analysis of efficacy endpoints will be based on the FAS. Supplemental analysis of efficacy endpoints may be performed using the efficacy evaluable analysis set. For the prostate cancer cohort, the confirmed PSA response rate and PSA-PFS will be based on the PSA evaluable analysis set.

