Tumor samples and blood will be collected at protocol-specified time points. Target expression by immunohistochemistry (IHC) and RNA will be performed retrospectively and there will be no subject preselection. Biomarker assessments from tumor tissue may include protein expression, gene expression, disease subtype classification, tumor microenvironment, and mutational profile. Assessments in blood samples may include cytokine measurements, immunoassays, and circulating nucleic acids. Methods of analysis may include IHC, polymerase chain reaction (PCR), next-generation sequencing, multiplex immunofluorescence, flow cytometry, immunoassays, and proteomic methodologies such as enzyme-linked immunosorbent assay (ELISA) and microvesicle assessment.

Safety Assessments

Safety assessments will include the surveillance and recording of AEs, physical examination findings, vital signs, concomitant medications, pregnancy testing, and laboratory tests. An ongoing, real-time review of subject safety and serious adverse events (SAEs) will be conducted by the sponsor's Drug Safety Department. Adverse event (AE) severity will be graded using the National Cancer Institute Common Terminology Criteria for Adverse Events (NCI CTCAE), version 5.

Statistical Methods

The primary analysis of the study will be performed separately for each cohort in Parts A, B, and C when all treated subjects in the cohort have been followed for at least 6 months or come off study, whichever comes first. The primary efficacy endpoint of confirmed ORR per RECIST v1.1 will be estimated for each cohort based on the full analysis set (FAS), comprising all subjects who received any amount of study treatment. The point estimate of ORR and 90% exact confidence intervals (CIs) using the Clopper-Pearson method will be provided for each cohort.

For the prostate cancer cohort, the confirmed PSA response rate and 90% exact CI will also be presented. The confirmed PSA response is defined as a reduction from baseline PSA level of at least 50%, measured twice ≥ 3 weeks apart.

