- Cohort 6, gastric and GEJ adenocarcinoma (Part A and Part B):
 - Must have pathologically-documented gastric or GEJ adenocarcinoma;
 - Must have unresectable locally advanced or metastatic disease;
 - Must have received prior platinum-based therapy;
 - Must have disease progression during or following systemic therapy;
 - Subjects with known human epidermal growth factor receptor 2 (HER2) overexpression must have received prior HER2-targeted therapy;
 - No more than 1 line of prior cytotoxic chemotherapy for their advanced disease;
 - Subjects may have received prior anti-PD(L)1 therapy, unless contraindicated.
- Cohort 7, CRPC (Part B only):
 - Must have histologically or cytologically confirmed adenocarcinoma of the prostate:
 - Subjects with components of small cell or neuroendocrine histology are excluded.
 - Must have metastatic castration-resistant disease:
 - Castration-resistant is defined as progressive disease following adequate medical or surgical (bilateral orchiectomy) castration and testosterone <50 ng/dL (<2.0 nM).
 - Must have been ≥28 days between cessation of androgen receptor-targeted therapy and start of study treatment;
 - Must have received no more than 1 prior line of 2nd generation androgen receptor-targeted therapy (eg, abiraterone acetate, enzalutamide, apalutamide,

- or darolutamide) for metastatic castration-sensitive prostate cancer (CSPC) or CRPC;
- No prior cytotoxic chemotherapy in the metastatic CRPC setting:
 - For subjects who received cytotoxic chemotherapy for CSPC, at least 6 months must have elapsed between last dose of chemotherapy and start of study treatment;
 - No more than 1 prior line of cytotoxic chemotherapy for CSPC
- Subjects with measurable and non-measurable disease are eligible if the following criteria are met:
 - A minimum starting PSA level ≥ 1.0 ng/mL;
 - Subjects with measurable soft tissue disease must have evidence of measurable soft tissue disease according to PCWG3 criteria. Previously normal (<1.0 cm) lymph nodes must have grown by ≥ 5 mm in the short axis to be considered to have progressed;
 - Subjects with nonmeasurable- disease (enrollment after interim analysis and no more than 15 subjects in total) must have documented rising PSA levels or appearance of new lesion according to PCWG3 ([Appendix L](#)):

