9.3.5.1. Primary Efficacy Analyses

The primary endpoint of this study for all tumor types is the confirmed ORR per investigator assessment. The ORR is defined as the proportion of subjects who achieve a confirmed CR or PR according to RECIST v1.1. The ORR of each cohort and its exact 2-sided 90% CI using the Clopper-Pearson method ([Clopper 1934](#)) will be calculated.

For prostate cancer, confirmed PSA response per investigator assessment is another primary endpoint. The confirmed PSA response is defined as a reduction from baseline PSA level of at

least 50%, measured twice ≥ 3 weeks apart. The confirmed PSA response rate and its exact 2-sided 90% CI using the Clopper-Pearson method ([Clopper 1934](#)) will be calculated.

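### Confirmed PSA response, a CRPC primary endpoint, is analysed on the PSA evaluable set although Section 9.3.1.7 puts all efficacy analyses on the FAS; the narrower set can only leave the response rate equal or raise it (minor)

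*Protocol*

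**What the plan says.** Protocol Section 9.3.1.7 defines the FAS as all treated subjects and states without qualification: "All efficacy analyses will be based on the FAS". The same section defines a PSA evaluable set: treated prostate cancer subjects who "had both baseline and at least one evaluable post-baseline PSA measurements". It does not say what that set is for.

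Section 9.3.5 repeats the FAS rule for the primary analysis of efficacy endpoints and then adds: "For the prostate cancer cohort, the confirmed PSA response rate and PSA-PFS will be based on the PSA evaluable analysis set". Section 9.3.5.1 gives PSA response its status: "For prostate cancer, confirmed PSA response per investigator assessment is another primary endpoint". In the synopsis (Statistical Methods), ORR is tied to the FAS. For prostate cancer the synopsis says only that "the confirmed PSA response rate and 90% exact CI will also be presented", with no analysis set named.

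For ORR, Section 9.2.1 has a missing-data rule: "Subjects who do not have at least 2 post-baseline response assessments (initial response and confirmation scan) will be counted as non-responders". Section 9.2.2, on confirmed PSA response, has no counterpart. Section 9.2.7 defines PSA-PFS as the time to "first occurrence of PSA progression or death, whichever comes first".

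The available SAP does not settle the matter. It is written for the original protocol of 22 April 2019, has no prostate cohort and no PSA endpoint, and puts all efficacy endpoints on the FAS (SAP Section 6.5).

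**The concern.** There are two separate issues. The first is wording: a general rule says all, a later section departs from it, and neither refers to the other.

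The second matters more, because it remains even if Section 9.3.5 is a deliberate exception. The subjects whom the PSA evaluable set removes are ones who cannot be responders. The removal can therefore only favour the reported rate. The two primary endpoints of one cohort would also treat the same very early dropout differently: a non-responder for ORR, absent for PSA response. The efficacy evaluable set, which the plan uses only for supplemental analyses, still keeps subjects who progress clinically or leave the study. The PSA evaluable set does not keep them unless a post-baseline PSA exists.

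At stake are the headline PSA response rate with its confidence interval and, for PSA-PFS, the visibility of very early deaths.

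**Working it through.** **Inputs**
- Cohort size 30, and a 2-sided 90% exact (Clopper-Pearson) interval: Protocol Sections 9.1 and 9.3.5.1.
- Confirmed PSA response: a fall of 50% or more from baseline, shown on two measurements 3 or more weeks apart (Section 9.2.2).
- PSA evaluable set: baseline plus one or more evaluable post-baseline values (Section 9.3.1.7).
- Number k of treated subjects outside that set: not given. I assume 1 to 3 of 30.

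**Step 1. Reproduce the plan's precision table.** The footnote to the table in Section 9.1 says it covers the CRPC PSA response rate. With 3, 6, 9, 12 and 15 responders of 30, the exact 90% intervals are 2.8 to 23.9, 9.1 to 35.7, 16.6 to 46.5, 25.0 to 56.6 and 33.9 to 66.1. These agree with the printed table.

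**Step 2. Direction.** A confirmed responder needs a baseline and two later PSA values, so every responder is inside the PSA evaluable set. With R responders, the FAS rate is R/30 and the PSA-set rate is R/(30 − k). The second is never smaller, and the two are equal only if k = 0 or R = 0.

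**Step 3. Who is dropped.** Only subjects with no evaluable post-baseline PSA or no baseline PSA. The latter is improbable, because Cohort 7 eligibility sets "A minimum starting PSA level" of 1.0 ng/mL (Section 4.1). A subject with exactly one post-baseline PSA stays in the set and counts as a non-responder, so the contrast with ORR does not extend to that subject.

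**Step 4. Size for the response rate.** The relative increase is 30/(30 − k) − 1, which is 3.4%, 7.1% and 11.1% for k = 1, 2 and 3, whatever the response rate. With R = 12:

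| k | Rate | 90% CI |
|---|---|---|
| 0 (FAS) | 12/30 = 40.0% | 25.0 to 56.6 |
| 1 | 12/29 = 41.4% | 25.9 to 58.3 |
| 2 | 12/28 = 42.9% | 26.9 to 60.0 |
| 3 | 12/27 = 44.4% | 28.0 to 61.8 |

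At the ends of the plan's range, with k = 3: 3/30 = 10.0% (2.8 to 23.9) becomes 3/27 = 11.1% (3.1 to 26.3), and 15/30 = 50.0% (33.9 to 66.1) becomes 15/27 = 55.6% (38.2 to 72.0).

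**Step 5. Size for PSA-PFS.** Suppose d subjects die before any post-baseline PSA, they are the only ones excluded, and nobody is censored before those deaths. Then S_FAS(t) = (1 − d/30) × S_evaluable(t). The factor is 29/30 = 0.967 for d = 1 and 28/30 = 0.933 for d = 2. A reported 50% would be 48.3% or 46.7% among all treated subjects.

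**The case against.** The strongest reply is that nothing here is truly ambiguous. Section 9.3.5 gives the FAS rule and the PSA rule in one paragraph, and the PSA evaluable set has no purpose other than PSA analyses. A specific rule after a general one is ordinary drafting, so a programmer would know which set to use. That largely stands: on wording alone, the defect is a missing exception clause in Section 9.3.1.7. It does not answer the one-sidedness.

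The effect is also likely to be small, and this stands too. PSA is scheduled every 3 weeks on treatment (Section 6.5.2), again at end of treatment (Section 6.6), and every 12 weeks after stopping for reasons other than progression (Section 6.7). To be excluded, a subject must miss every evaluable draw after baseline, which mainly means a very early death, withdrawal or loss. Even at k = 3 the shift of 4.4 points lies inside an interval about 32 points wide. Analysis-set sizes will be tabulated (Section 9.3.2), so a reader could recompute the FAS rate.

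Three stronger readings are tempting, and the documents do not support them:
- A reader might infer that the denominator influences whether the cohort continues. The interim futility count is CR or PR (Section 9.3.9, Table 20 footnote), and the sample size rests on no formal test.
- A reader might infer that PSA-PFS leaves an early death undefined. Section 9.2.7 makes death an event and does not require an earlier PSA value. The subject is lost through the analysis set, not through the definition.
- A reader might carry over the Day 1 censoring in Section 9.2.5. That rule concerns a missing tumour evaluation for PFS, and the protocol never applies it to PSA-PFS.

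Finally, the protocol defers detail to a SAP finalised before database lock. A later SAP may deal with this; the available one cannot, having no prostate cohort.

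**Conclusion.** The point holds as a minor one. The direction is certain and follows from the protocol's own definitions: the PSA response rate on the PSA evaluable set equals or exceeds the rate among all treated CRPC subjects. The size is not known. With the assumed 1 to 3 of 30 excluded and 12 responders, the overstatement is 1.4 to 4.4 percentage points; across 3 to 15 responders it is 0.3 to 5.6 points. It is zero if every treated subject has a baseline and an evaluable post-baseline PSA. For PSA-PFS the consequence is limited to deaths before the first post-baseline PSA, under the assumptions in Step 5. What is affected is how one primary endpoint and one secondary endpoint are estimated and reported.

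**What to change.** - **PSA response:** make the FAS the primary set for the confirmed rate, and count subjects without a baseline or without two qualifying post-baseline PSA values as non-responders. This matches the treatment of ORR in the same cohort.
- **PSA-PFS:** analyse on the FAS, with death an event as Section 9.2.7 already defines.
- **PSA evaluable set:** keep it for a supplementary analysis of both endpoints.
- **Text:** align Protocol Sections 9.3.1.7 and 9.3.5 (about a sentence each), and carry the rule into the SAP update.

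The cost is low. The SAP must gain prostate and PSA text in any case, no new data are needed, and site conduct does not change, so under Protocol Section 9.3 the SAP can carry the rule without a separate protocol amendment. The one downside is a slightly less favourable PSA response rate if the present rule would have excluded any treated subject.
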